Target population	Patients with biochemical recurrence after prostatectomy who are considered candidates for salvage radiation therapy (XRT) 
• Adult male ≥ 18 years of age• Patients must have histologically confirmed adenocarcinoma of the prostate gland• Patients must have received primary treatment with radical prostatectomy.• Patients must have evidence of biochemical (PSA) relapse after prostatectomy, defined by one rise in PSA above a baseline detectable value (≥ 0.05 ng/mL) using measurements taken at least 4 weeks apart from each other (all PSA values must be within 12 months of study entry).

- Patients must have pathological Gleason (pG) sum 8-10; or pG sum 7 and either pT3 or R1 disease (*i.e. positive margins.*).
- Patients must have an absolute PSA level between ≥ 0.05 and < 0.7 ng/mL at the time of study entry.
- Patients must have non-metastatic (M0) disease, as defined by a lack of metastases seen on CT scan of the abdomen/pelvis and whole-body radionuclide ^{99}Tc bone scan, (or sodium fluoride PET scan) taken within 3 months of study entry.
- Patients must have had node negative (pN0) disease found at the time of surgery. If a nodal dissection was not performed at the original surgery then patients must be N0, as defined by a lack of radiographic or clinical evidence of local-regional tumor recurrence, including lack of pelvic lymph nodes ≥ 2 cm in short-axis diameter.
- Patients must have non-castrate levels of serum testosterone (≥ 150 ng/dL), as evidence by any testosterone taken within six (6) months of enrollment
- Patients must not have previously received hormonal therapy (LHRH agonist/antagonist, antiandrogen, or both), with the exception of neoadjuvant or adjuvant hormones given in conjunction with prostatectomy. In such cases, hormone therapy must have been administered for ≤ 6 months, discontinued ≥ 6 months ago, and serum testosterone must be ≥ 150 ng/dL.
- Patients must have ECOG performance status of 0-1, and life expectancy ≥ 3 years.
- Patients must have laboratory test results within the ranges listed below:
 - WBC $\geq 3000/\text{mm}^3$
 - Granulocytes $\geq 1500/\text{mm}^3$
 - Hemoglobin $\geq 9\text{ g/dL}$
 - Platelets $\geq 100,000/\text{mm}^3$
 - Bilirubin $\leq 1.8\text{ mg/dL}$
 - ALT and AST ≤ 2.5 times the institutional upper limit of normal
 - Creatinine $\leq 1.8\text{ mg/dL}$ OR a calculated creatinine clearance $\geq 60\text{ mL/hr}$

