3.3 Inclusion Criteria

To be included in this study, patients should meet all of the following criteria:

- Willing and able to provide written informed consent and HIPAA authorization for the release of personal health information.

NOTE: HIPAA authorization may be either included in the informed consent or obtained separately.

- Males aged 18 years of age and above
- Patients must have histologically confirmed adenocarcinoma of the prostate gland
- Patients must have received primary treatment with radical prostatectomy.
- Patients must have evidence of biochemical (PSA) relapse after prostatectomy, defined by one rise in PSA above a baseline detectable value (≥ 0.05 ng/mL) using measurements taken at least 4 weeks apart from each other (all PSA values must be within 12 months of study entry).
- Patients must have pathological Gleason (pG) sum 8-10; or pG sum 7 and either pT3 or R1 disease (*i.e. positive margins*).
- Patients must have an absolute PSA level between ≥ 0.05 and < 0.7 ng/mL at the time of study entry.
- Patients must have non-metastatic (M0) disease, as defined by a lack of metastases seen on CT scan of the /abdomen/pelvis and whole-body radionuclide ^{99}Tc bone scan, (or sodium fluoride PET scan) taken within 3 months of study entry.
- Patients must have had node negative (pN0) disease found at the time of surgery. If a nodal dissection was not performed at the original surgery then patients must be N0, as defined by a lack of radiographic or clinical evidence of local-regional tumor recurrence, including pelvic lymph nodes ≥ 2 cm in short-axis diameter.

- Patients must have non-castrate levels of serum testosterone (≥ 150 ng/dL).
- Patients must not have previously received hormonal therapy (LHRH agonist, antiandrogen, or both), with the exception of neoadjuvant or adjuvant hormones given in conjunction with prostatectomy. In such cases, hormone therapy must have been administered for ≤ 6 months, discontinued ≥ 6 months ago, and serum testosterone must be ≥ 150 ng/dL.
- Patients must have ECOG performance status of 0-1, and life expectancy ≥ 3 years.
- Patients must have laboratory test results within the ranges listed below within 4 weeks of enrollment:
 - WBC $\geq 3000/\text{mm}^3$
 - Granulocytes $\geq 1500/\text{mm}^3$
 - Hemoglobin $\geq 9\text{ g/dL}$
 - Platelets $\geq 100,000/\text{mm}^3$
 - Bilirubin $\leq 1.8\text{ mg/dL}$
 - ALT and AST ≤ 2.5 times the institutional upper limit of normal

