 - Creatinine $\leq 1.8\text{ mg/dL}$ OR a calculated creatinine clearance $\geq 60\text{ mL/hr}$
- Patients must be disease-free from prior malignancies for ≥ 3 years, with the exception of non-melanoma skin cancers and superficial urothelial cancers.
- Patients must have the ability to swallow the study drug whole as a tablet or capsule.
- Throughout study, male patient and his female partner who is of childbearing potential must use 2 acceptable methods of birth control (1 of which must include a condom as a barrier method of contraception) starting at screening and continuing throughout the study period and for 3 months after final study drug administration or per local guidelines where these require additional description of contraceptive methods. Two acceptable methods of birth control thus include the following:
 - Condom (barrier method of contraception); AND
 - One of the following is required:
 - Established and ongoing use of oral, injected, or implanted hormonal method of contraception by the female partner.
 - Placement of an intrauterine device or intrauterine system by the female partner.
 - Additional barrier method: Occlusive cap (diaphragm or cervical/vault caps) with spermicidal foam/gel/film/cream/suppository by the female partner.
 - Tubal ligation in the female partner.
 - Vasectomy or other procedure resulting in infertility (eg, bilateral orchiectomy), for > 6 months.
- Throughout the study, patients must use a condom if having sex with a pregnant woman.
- The patient was informed about the positive survival results of the RTOG 96-01 clinical trial, and has elected to forgo treatment with high-dose bicalutamide.

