3.4 Exclusion Criteria

Patients that meet any of the criteria listed below will not be eligible for study entry:

- Currently active second malignancy
- Primary treatment with radiation therapy.
- Radiographic or clinical evidence of regional tumor nodal recurrence, including pathological pelvic lymph nodes ≥ 2 cm in short-axis diameter. Radiographic evidence of distant metastases is also an exclusion.
- Concurrent use of other antiandrogens, estrogen-like agents, or 5a-reductase inhibitors.
- Use of systemic corticosteroids equivalent to prednisone 10 mg/day or higher at the time of study entry (inhaled corticosteroids are permitted).
- Concurrent use of other anti-cancer agents or treatments.
- Serious concurrent medical illnesses (including uncontrolled major cardiac, pulmonary, Child-Pugh C liver or psychiatric diseases) or active major infections (including HIV, Hepatitis A-C).
- Clinically significant cardiovascular disease including:
 - Myocardial infarction within 6 months of Screening visit.
 - Uncontrolled angina within 3 months of Screening visit.
 - Congestive heart failure New York Heart Association (NYHA) class 3 or 4, or subjects with history of congestive heart failure NYHA class 3 or 4 in the past, or history of anthracycline or anthracenedione (mitoxantrone) treatment, unless a screening echocardiogram or multi-gated acquisition scan (MUGA) performed within three months of the Screening visit results in a left ventricular ejection fraction that is $\geq 45\%$.
 - History of clinically significant ventricular arrhythmias (e.g., ventricular tachycardia, ventricular fibrillation, torsade de pointes).
 - Prolonged corrected QT interval by the Fridericia correction formula (QTcF) on the screening electrocardiogram (ECG) > 470 msec.
 - History of Mobitz II second degree or third degree heart block without a permanent pacemaker in place.
 - Hypotension (systolic blood pressure < 86 mmHg or bradycardia with a heart rate of < 50 beats per minute on the Screening ECG, unless pharmaceutically induced and thus reversible (i.e. beta blockers).
 - Uncontrolled hypertension as indicated by a resting systolic blood pressure > 170 mmHg or diastolic blood pressure > 105 mmHg at the screening visit.
- Medications which lowers seizure threshold.

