- History of seizure or any condition that may predispose to seizure including, but not limited to underlying brain injury, stroke, primary brain tumors, brain metastases, or alcoholism. Also, history of loss of consciousness or transient ischemic attack within 12months of enrollment (Day 1 visit).
- Patients taking medications that may have adverse interactions with enzalutamide (see Appendix B).

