All subjects considered for enrollment in the study must complete an IRB-approved informed consent prior to any study-specific procedures being performed.

To register a patient, the participating site must contact the Lead Center's Study Coordinator about a potential candidate prior to sending documents. Once acknowledgement is made, the following documents must be completed and faxed to [contact]) or e-mailed to the lead site:

- Signed patient consent form
- Eligibility checklist signed by the participating center PI or Co-I
- Copies of all source documentation verifying eligibility criteria

The Lead Site will review the documents to confirm eligibility. To complete the registration process, the Lead Center will:

- Assign a patient study number
- Randomize the patient onto a treatment arm
- Register the patient on the study with the Sidney Kimmel Comprehensive Cancer Center's Clinical Research Office.
- Fax or e-mail the unique patient study number and assigned study arm to the participating site.

Treatment must not commence until the patient has been registered with the Sidney Kimmel Comprehensive Cancer Center's Clinical Research Office and randomization has been completed by the coordinating center.

4.1.2 *Multicenter/Participating site registration*

Central registration for this study will take place at *SKCCC, Johns Hopkins University*.

Patient registration at each study site/institution will be conducted according to the institution's established policies. Before registration, patients will be asked to sign and date an Institutional Review Board (IRB)-approved consent form and a research authorization/HIPAA form. Patients must be registered with their local site/institution and also with the sponsor or Lead Site before beginning any treatment.

4.1.3 *Randomization*

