Abbreviations: CBC, complete blood count; CT, computerized tomography; EKG, electrocardiogram; MRI, magnetic resonance imaging; PSA, prostate-specific antigen; Mos, Month

1. All evaluations should be conducted within 30 days prior to registration/randomization. The exception to this is the radiologic evaluations and informed consent, which can be performed within 90 days prior to day 1.
2. CBC which includes WBC (with differential), platelets, Hgb, and Hct
3. Chemistries include albumin, alkaline phosphatase, total bilirubin, BUN, calcium, chloride, creatinine, glucose, sodium, potassium, total protein, SGOT [AST], and SGPT [ALT].
4. Those patients coming off study prior to PSA progression (i.e. for toxicity, etc.) should be evaluated for PSA levels every 3 months until PSA progression occurs.
5. ECGs may also be performed as clinically indicated throughout the study.
6. Radiologic evaluations (CT/MRI and bone scan) and chest x-ray (if applicable) should be conducted at PSA progression. Scans can also be obtained sooner as clinically indicated.
7. Quality-of-life (QoL) tools will include FACT-P, EORTC QLQ-C30/QLQ-PR25, and SHIM.
8. Patients should remain on study until PSA progression. This is defined as a PSA value ≥ 0.2 ng/mL above nadir that is confirmed by a second consecutive PSA value ≥ 8 weeks later which is higher (and ≥ 0.4 ng/mL). Patients should remain on study until the confirmatory PSA.
9. The total length of the study is 18 months for full enrollment and 24-months of follow-up for the last patient or 42 months. Patients who have 24-months of follow-up following treatment will continue to be followed for PSA determinations only and should remain on study until PSA progression or study end at month 42 whichever comes first.
10. To be conducted 2 months after the patient comes off study.
11. In patients who have consented, a tumor tissue block should be requested for banking, preferably from the prostatectomy specimen. If not available, a tissue block from the prostate biopsy should be submitted. In addition, a normal tissue block from the same patient (preferably from the prostatectomy) should be requested for banking. This only applies to the lead site (JHU).
12. Drug and diary review and dispensing may be done prior to or indicated day.
13. SRT to start 61 days (+/- 3 weeks) after Day 1. SRT will be delivered Monday-Friday
14. Decipher Test can be completed at any time before treatment ends on Day 180.

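### The renal inclusion criterion gives creatinine clearance in mL/hr, so as written it excludes practically no man with creatinine above 1.8 mg/dL

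*Combined protocol and SAP*

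**What the plan says.** The laboratory criteria in section 3.3 are mandatory: "Patients must have laboratory test results within the ranges listed below within 4 weeks of enrollment". The renal line in that list is "Creatinine $\leq 1.8\text{ mg/dL}$ OR a calculated creatinine clearance $\geq 60\text{ mL/hr". The synopsis (Target population) has the same line, again with "OR a calculated creatinine clearance $\geq 60\text{ mL/hr". The two places agree with each other, and nowhere do the documents give the limit in mL/min or name a formula for calculating clearance.

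No other entry rule carries a renal number. Several could still keep out a man with severe renal disease:

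- Section 3.4 excludes serious concurrent illness, with examples that do not include renal disease: "Serious concurrent medical illnesses (including uncontrolled major cardiac, pulmonary, Child-Pugh C liver or psychiatric diseases".
- Section 3.4 also excludes "any condition that may predispose to seizure including, but not limited to underlying brain injury".
- Section 3.3 requires hemoglobin of at least 9 g/dL and states "Patients must have ECOG performance status of 0-1, and life expectancy ≥ 3 years".

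Eligibility is checked centrally. Under section 4.1.1, "The Lead Site will review the documents to confirm eligibility".

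**The concern.** A clearance limit of 60 is normally expressed per minute. Stated per hour, it is 60 times lower and falls far below any value at which a man could plausibly be considered for this trial. Because the criterion is met by either part, a clearance part that nearly everyone meets also disables the creatinine part. The line looks like a renal safeguard, but as written it screens out practically nobody.

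What is at stake is the correctness of a binding eligibility limit, and with it the safety of a small and possibly empty group: men with creatinine above 1.8 mg/dL whose clearance lies between 1 and 60 mL/min. Under the written rule they may enter; under the presumed rule they may not. Men at or below 1.8 mg/dL qualify on the creatinine part whatever the unit.

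**Working it through.** The threshold is simply stated, with no derivation to reproduce, so the check is a unit conversion followed by an illustration.

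**Step 1: unit conversion.** Input: 60 mL/hr (synopsis; section 3.3). 60 mL/hr ÷ 60 min/hr = 1 mL/min. The presumed limit, 60 mL/min, would be 60 × 60 = 3,600 mL/hr.

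**Step 2: who fails the line as written.** Failing requires creatinine above 1.8 mg/dL *and* clearance below 1 mL/min. The protocol names no formula, so I assume the Cockcroft-Gault form for men, clearance (mL/min) = (140 − age) × weight / (72 × creatinine). Ages and weights are also my assumptions. Setting clearance to 1 mL/min, a man fails only if his creatinine exceeds (140 − age) × weight / 72:

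| Age | Weight (kg) | Creatinine needed to fail (mg/dL) |
|---|---|---|
| 80 | 60 | 60 × 60 / 72 = 50.0 |
| 65 | 80 | 75 × 80 / 72 = 83.3 |
| 55 | 110 | 85 × 110 / 72 = 129.9 |

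Even at a creatinine of 10 mg/dL, the man of 65 and 80 kg has 83.3 / 10 = 8.3 mL/min and passes.

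**Step 3: would the corrected line restrict entry?** At 60 mL/min, a man with creatinine just above 1.8 mg/dL passes only if (140 − age) × weight is at least 60 × 1.8 × 72 = 7,776. The minimum weight is therefore 7,776 / (140 − age): 91.5 kg at 55, 103.7 kg at 65, 111.1 kg at 70 and 119.6 kg at 75. So the unit decides eligibility. For example, at age 65 and creatinine 1.9 mg/dL:

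- 80 kg: 83.3 / 1.9 = 43.9 mL/min. Passes as written, fails at 60 mL/min.
- 110 kg: (75 × 110 / 72) / 1.9 = 114.6 / 1.9 = 60.3 mL/min. Passes under both.

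**Step 4: how many men.** Section 10.4.1 reports 80 men enrolled by April 2019 and a revised target of 96, leaving at most 96 − 80 = 16 at that date. Both groups count, because the 80 may have entered under the same line. The documents do not say how many had creatinine above 1.8 mg/dL.

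**Step 5: effect on the analysis.** The sample size in section 10.4.1 rests on 2-year FFPP of 60% and 80%, a hazard ratio of 0.44, one-sided alpha of 0.1, 90% power, 39 events and 15% loss. None depends on the renal criterion. The intention-to-treat population (section 10.2.1) is everyone randomized, whatever his renal function, and the criterion applies equally to both arms.

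**The case against.** The strongest reply is that this is a slip of the pen with no consequence. Experienced staff will read the limit as mL/min. The participating site signs an eligibility checklist and sends source documents, which the lead site reviews before registration. A man with very poor renal function would also have to meet the performance-status, life-expectancy and hemoglobin requirements and avoid the serious-illness exclusion. Creatinine is in the panel repeated on treatment and in follow-up (section 5.2; Table 1, footnote 3: "Chemistries include albumin, alkaline phosphatase, total bilirubin, BUN, calcium, chloride, creatinine"). The documents describe no renal-specific harm from enzalutamide. And the intended unit is itself an inference.

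Most of this stands, and it is why the point is minor. It does not remove the error. Central review compares each man with the written limit, and the written limit is wrong. The other criteria may exclude some men, but none says at what renal function. A limit that works only if every reader silently changes its unit should be corrected.

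A reader might infer more than the documents support:

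- *That the trial has no protection against enrolling men with renal failure.* The general criteria above may well exclude many of them. What fails is the numeric renal criterion.
- *That men with poor renal function were in fact enrolled, or harmed.* The documents report no baseline creatinine values.
- *That the efficacy comparison is compromised.* Step 5 shows no route by which it could be.

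**Conclusion.** The point holds as a minor eligibility and safety correction. The conversion to 1 mL/min is exact and needs no assumption, and the same unit in two separate places makes a PDF reading error unlikely. That the criterion excludes practically no man above 1.8 mg/dL follows from the conversion and the either/or wording. The creatinine values of roughly 50 to 130 mg/dL needed to fail, and the minimum weights under a corrected limit, depend on the assumed formula, ages (55 to 80) and weights (60 to 110 kg). That 60 mL/min was intended is an inference for the sponsor to confirm. The number of men affected is unknown and may be zero.

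**What to change.** Once the sponsor confirms that 60 mL/min is intended, change mL/hr to mL/min in the synopsis (Target population) and in section 3.3. The eligibility checklist should carry the same unit. The cost is one unit in two places of the protocol, which can go into any amendment.

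Optionally, look up baseline creatinine for the men already enrolled, using values collected at screening (section 5.1), to see whether any exceeded 1.8 mg/dL with clearance below the corrected limit. If one did, note it for safety review. He met the criterion as written, stays in the intention-to-treat population, and no analysis changes.

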3.4 Exclusion Criteria

Patients that meet any of the criteria listed below will not be eligible for study entry:

- Currently active second malignancy
- Primary treatment with radiation therapy.
- Radiographic or clinical evidence of regional tumor nodal recurrence, including pathological pelvic lymph nodes ≥ 2 cm in short-axis diameter. Radiographic evidence of distant metastases is also an exclusion.
- Concurrent use of other antiandrogens, estrogen-like agents, or 5a-reductase inhibitors.
- Use of systemic corticosteroids equivalent to prednisone 10 mg/day or higher at the time of study entry (inhaled corticosteroids are permitted).
- Concurrent use of other anti-cancer agents or treatments.
- Serious concurrent medical illnesses (including uncontrolled major cardiac, pulmonary, Child-Pugh C liver or psychiatric diseases) or active major infections (including HIV, Hepatitis A-C).
- Clinically significant cardiovascular disease including:
 - Myocardial infarction within 6 months of Screening visit.
 - Uncontrolled angina within 3 months of Screening visit.
 - Congestive heart failure New York Heart Association (NYHA) class 3 or 4, or subjects with history of congestive heart failure NYHA class 3 or 4 in the past, or history of anthracycline or anthracenedione (mitoxantrone) treatment, unless a screening echocardiogram or multi-gated acquisition scan (MUGA) performed within three months of the Screening visit results in a left ventricular ejection fraction that is $\geq 45\%$.
 - History of clinically significant ventricular arrhythmias (e.g., ventricular tachycardia, ventricular fibrillation, torsade de pointes).
 - Prolonged corrected QT interval by the Fridericia correction formula (QTcF) on the screening electrocardiogram (ECG) > 470 msec.
 - History of Mobitz II second degree or third degree heart block without a permanent pacemaker in place.
 - Hypotension (systolic blood pressure < 86 mmHg or bradycardia with a heart rate of < 50 beats per minute on the Screening ECG, unless pharmaceutically induced and thus reversible (i.e. beta blockers).
 - Uncontrolled hypertension as indicated by a resting systolic blood pressure > 170 mmHg or diastolic blood pressure > 105 mmHg at the screening visit.
- Medications which lowers seizure threshold.
- History of seizure or any condition that may predispose to seizure including, but not limited to underlying brain injury, stroke, primary brain tumors, brain metastases, or alcoholism. Also, history of loss of consciousness or transient ischemic attack within 12months of enrollment (Day 1 visit).
- Patients taking medications that may have adverse interactions with enzalutamide (see Appendix B).

3.5 Inclusion of Minorities

Men of all races and ethnic groups are eligible for this trial.

